#### 5.2. Exclusion Criteria

- Participant is, in the opinion of the investigator, mentally or legally incapacitated, preventing informed consent from being obtained, or cannot read or understand the written material
- Participant is unable to perform spirometry or plethysmography maneuvers
- Healthy participants with a previous clinical diagnosis of respiratory disease, psychological disorder(s) or head trauma

DATE: November 15, 2024

- For the subset of asthmatics identified as underperceivers and undergoing brain fMRI, participants with a previous clinical diagnosis of psychological disorder(s) or head trauma
- Participant has an implanted mechanically, electrically or magnetically activated device or any metal in their body, which cannot be removed, including but not limited to pacemakers, neurostimulators, biostimulators, implanted insulin pumps, aneurysm clips, bioprosthesis, artificial limb, metallic fragment or foreign body, shunt, surgical staples (including clips or metallic sutures and/or ear implants.) (At the discretion of the MRI Technologist/3T Manager).
- In the investigator's opinion, participant suffers from any physical, psychological or other condition(s) that might prevent performance of the MRI, such as severe claustrophobia.
- Patient is pregnant
- Healthy participants with a previous clinical diagnosis of a respiratory disease or a history of head trauma or psychological disorders that may affect the ability to participate or follow instructions during the MRI. The healthy volunteer has to be a never smoker.

# 6. STUDY PROCEDURES

# 6.1. Screening Procedures for Study Entry

Eligibility for this study will be determined by the participant's clinical history, including respiratory disease and medication history. In addition, the investigator or designate shall discuss with each participant the nature of the study, its requirements and its restrictions, and an informed consent document will be signed. Each participant will be assigned a unique Study Number that will serve to identify participant study documentation. If a participant fails to qualify for enrollment, his/her Study Number may not be reused for another participant.

Participants performing fMRI will be either healthy volunteers or have been identified as having poor asthma control and demonstrate inaccurate perception of their asthma symptoms using asthma control and quality of life questionnaires. Specifically, these asthmatic participants are unable to sense sensations of dyspnea during asthma flair-ups. Participants who have suffered from a brain or head injury or participants that have diagnosed with an anxiety and depression disorder will be excluded from this part of the study.

# 6.2. Vital Signs

Vital signs will consist of sitting blood pressure, respiratory rate, heart rate, oral temperature, height and weight. Blood pressure will be taken using an appropriately sized cuff.

# **6.3. Pulmonary Function Tests**

Full pulmonary function tests including spirometry (Appendix I), plethysmography, and DLCO (Appendix II) will be performed according to ATS guidelines. MedGraphics Elite Series, MedGraphics Corporation. St. Paul, MN USA and/or nDD EasyOne Spirometer,

DATE: November 15, 2024

nDD Medical Technologies Inc. Andover, MA USA will be used. All measurements will be performed in the Pulmonary Function Laboratory at Robarts Research Institute.

LCI will be performed using the nDD Easy-One Pro Lab. Participants breathe normally into a mouthpiece connected to the device for 3-5 minutes.

#### 6.4. FOT

FOT measures respiratory system function and will be performed according to European Respiratory Society (ERS) Guideline (Oostveen et al., Eur Respir J 2003; 22: 1026–1041) using a tremoFlo® C-100 airwave oscillometry system (Thorasys Thoracic Medical Systems Inc.; Montreal, QC, Canada, License number 92761). This is as follows; Participants breathe normally through a disposable standard antibacterial/antiviral filter as used in spirometry, and are in an upright and seated position. The participant's hands will support cheeks and a noseclip applied to the nose during the measurement. Three repeated measurements of 16 seconds each will then be acquired and measures of lung function evaluated using tremoFlo software. Since respiratory mechanics are slightly altered depending on supine or upright position, with an increase in respiratory system resistance (Rrs) and decrease in low frequency reactance (Xrs), in the supine position, FOT measurements will be obtained in the standard upright position for comparison with predicted values, but will then be obtained in the supine position to relate to the MRI data.

All measurements will be performed in the Pulmonary Function Laboratory at Robarts Research Institute (Appendix IV).

# 6.5. Fractional Exhaled Nitric Oxide (FeNO)

FeNO will be measured pre-bronchodilator using the NIOX VERO® (Circassia Pharmaceuticals Inc, Morrisville, NC, USA, License number 98844). Participants will be seated upright and given the mouthpiece of the NIOX VERO®. Participants will be instructed to breathe out fully, then bring the mouthpiece to their lips to create a seal around the mouthpiece. Participants are then asked to inhale deeply to total lung capacity, then exhale slowly and completely into the mouthpiece.

FeNO measurements will be performed at Robarts Research Institute in the Pulmonary Function Laboratory (Appendix V).

#### 6.6. MDCT

Thoracic low dose MDCT will be performed with the same inhalation breath-hold volume and maneuver ( $N_2$  only) used for MRI to obtain participant-specific high resolution images of lung anatomy (tissue structure and airway morphology). CT imaging will be performed using an Aquilion ONE CT scanner (Canon Medical Systems USA, INC., Tustin, CA, USA) or a Lightspeed VCT CT scanner (General Electric, Waukesha WI, USA) at either Robarts Research Institute in London, Ontario or at University Hospital, located next door to Robarts Research Institute. Participants will be scanned in the supine position and during inspiration breath-hold after inhaling 1L of  $N_2$  in order to match CT and MRI breath-hold volumes and anatomy.

# 6.7. General MRI Testing Procedures

Participants will undergo MRI in the supine position. MRI localizing scans will be performed prior to administration of the hyperpolarized Xe. One of three Xe chest coils covering the entire thorax will be used. Participants will be instructed to take a deep

DATE: November 15, 2024

breath, exhale completely, then inhale the Xe completely and hold their breath for 13-16 s. The chest coils which may be used are:

- 1. 129Xe Radio Frequency Coil for Human Lung Imaging
- 2. CMRS Flexible Lung Coil (Clinical MR Solutions)
- 3. 129Xe Lung Coil (RAPID Biomedical)

For the subset of participants undergoing fMRI acquisition, they will be placed in the supine position, and their head will be covered in an elliptical head coil (shown below). Participants will be instructed to remain motionless during the 20-minute scanning process.

Head Coil

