# MULTI-DETECTOR ROW COMPUTED TOMOGRAPHY (MDCT)

Thoracic low dose MDCT will be performed with the same inhalational breath-hold volume and maneuver (nitrogen ( $N_2$ ) gas only) used for MRI. CT imaging will be performed using either an Aquilion ONE CT scanner (Canon Medical Systems USA, INC., Tustin, CA, USA) or a Lightspeed VCT CT scanner (General Electric, Waukesha WI, USA) at either Robarts Research Institute in London, Ontario or at University Hospital, located next door to Robarts Research Institute. Participants will be scanned in the supine position and during inspiration breath-hold from functional residual capacity (FRC) after inhaling 1L of  $N_2$  gas as previously described in order to match CT and MRI breath-hold volumes and anatomy.

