#### 4.1.2. MRI

Participants will be screened for contraindications by the MR technologist. Prior to being made comfortable on the scanner bed in the magnet, participants will be required to do a 16-second breath-hold test using a dose bag containing air similar to that used for xenon imaging. This maneuver ascertains their ability at that time to undergo administration of Xe gas and a 16-second breath-hold for the MR study. They will be placed in the 3T MR scanner with one of three Xe chest coils fitted over their torso and chest. Hearing protection will be provided to each participant to muffle the noise produced by the gradient RF coils. A pulse oximeter lead will be attached to all of the participants to monitor their heart rate and oxygen saturation. MRI will be performed for up to a period of 30 minutes. All participants will have supplemental oxygen provided via nasal cannula at a flow-rate of 2 liters per minute during the scanning process.

Once comfortable on the MRI scanner table, participants will undergo 1 MRI session containing acquisition of several images as follows:

Proton (H) imaging – participants will inhale a 1 litre gas mixture containing medical grade nitrogen (N2). This is performed in order to match breath hold volumes and anatomy with Xe images. Breath hold will be up to 16 seconds.

Static ventilation imaging – participants will inhale a 1 litre gas mixture containing Xe and or He (5 ml/kg body weight) mixed with helium-4 (He) from a 1 litre bag. Breathhold will be up to 16 seconds.

Diffusion-weighted imaging – participants will inhale a 1 litre gas mixture containing Xe and or He (5 ml/kg body weight) mixed with He from a 1 litre bag. Breath-hold will be up to 16 seconds.

Dissolved phase imaging – participants will inhale a 1 litre gas mixture containing Xe mixed with He from a 1 litre bag. Breath-hold will be up to 16 seconds.

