# 4.1.6. Multi-Detector Computed Tomography (MDCT)

Thoracic low dose MDCT will be performed with the same inhalation breath-hold volume and maneuver ( $N_2$  gas only) used for MRI to obtain participant-specific high resolution images of lung anatomy (tissue structure and airway morphology). CT imaging will be performed using an Aquilion ONE CT scanner (Canon Medical Systems USA, INC., Tustin, CA, USA) or a Lightspeed VCT CT scanner (General Electric, Waukesha WI, USA) at either Robarts Research Institute in London, Ontario or at University Hospital, located next door to Robarts Research Institute. Participants will be scanned in the supine position and during inspiration breath-hold after inhaling 1L of  $N_2$  in order to match CT and MRI breath-hold volumes and anatomy.

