#### 7. STUDY PARAMETERS

#### 7.1. Evaluation of Disease

# 7.1.1. Pulmonary Function Testing

The FEV1 and FVC will be recorded according to ATS guidelines. Parameters to be assessed include but are not limited to: total lung capacity (TLC), functional residual capacity (FRC) and DLco. FRC measures the volume in the lungs when the muscles of respiration are relaxed. FOT measurements will be recorded according to ERS recommendations (Oostveen et al., Eur Respir J 2003; 22: 1026–1041). Input impedance is calculated as the ratio of pressure and flow signals and are given as Rrs and reactance Xrs at each oscillation frequency as well as comparison to predicted values. Additional outcomes that are provided from this measurement include tidal volume, respiratory rate, and resonant frequency.

Frequency dependence of Rrs is an index of ventilation heterogeneity, and low frequency reactance (6 Hz) can be used as an index of airway closure (Lutchen et al., 20xx) and we are investigating if this corresponds to the occurrence of ventilation defects. We will assess the frequency dependence by subtracting Rrs at 19 Hz from Rrs at 6 Hz. Furthermore, low frequency elastance at 6 Hz can be used as an index of airway closure indicative of the presence of low or near zero ventilation.

FeNO will be measured one time according to instructions from the machine which is set to perform to ATS guidelines. The FeNO value will be displayed on the machine and recorded in source documents, it is a valuable tool in the assessment of airway inflammation.

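### The protocol says CT and MRI use the same breath-hold, but section 6.7 starts 129Xe MRI from complete exhalation and the synopsis starts CT from FRC

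*Protocol*

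**What the plan says.** **MRI.** Section 6.7 tells participants to take a deep "breath, exhale completely, then inhale the" 129Xe fully and hold for 13-16 s. Section 4.1.2 sets the inhaled volume ("participants will inhale a 1 litre gas mixture containing" the imaging gas) but no starting lung volume. It says the 1H scan, done with 1 L of nitrogen, is meant to match the 129Xe images. It gives no starting volume for that scan either.

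**CT.** The synopsis MDCT section opens: "Thoracic low dose MDCT will be performed with the same inhalational breath-hold volume and maneuver" as MRI, with nitrogen only. It then specifies the scan "during inspiration breath-hold from functional residual capacity (FRC) after inhaling 1L of" nitrogen. Section 4.1.6 repeats the equivalence ("Thoracic low dose MDCT will be performed with the same inhalation breath-hold volume and maneuver") and gives its purpose: "in order to match CT and MRI breath-hold volumes and anatomy". Section 6.6 says the same. Neither 4.1.6 nor 6.6 names a starting lung volume.

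**Use of the pairing.** Section 8 plans Pearson correlations of VDP and TCV with CT WA%, among other measurements. The second hypothesis in section 3 is that ventilation abnormalities relate to airway morphology, validated by CT and histology.

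**The concern.** The protocol makes three statements: MRI starts from complete exhalation, CT starts from FRC, and the two maneuvers are the same. At most two of them can be true together. All three MDCT sections give matching as the reason for the CT breath-hold, so a difference in starting volume defeats the purpose that the protocol itself states.

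The difference would not be a constant offset, because expiratory reserve differs from person to person. TCV is itself a lung volume and enters the planned correlations directly. The visit schedule in section 4.1 lists CT at the baseline visit only, so a CT-MRI pair acquired at unequal volumes would not be replaced by a later scheduled one. Staff who read only section 6.7 and staff who read only the synopsis could also coach differently.

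**Working it through.** The protocol states no figure to reproduce. The check is a comparison of texts followed by one line of algebra.

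**1. Are the two starting points different in the protocol's own terms?** Section 7.1.1 says that "FRC measures the volume in the lungs when the muscles of respiration are relaxed". For the DLco test, Appendix II has the participant exhale maximally to reach residual volume. The protocol therefore distinguishes a relaxed end-expiratory volume from the volume after maximal exhalation. Complete exhalation in section 6.7 corresponds to the second.

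**2. Volume at imaging, each instruction taken literally.**

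- MRI (section 6.7 with 4.1.2): RV + 1 L
- CT (synopsis MDCT): FRC + 1 L
- CT minus MRI: (FRC + 1) - (RV + 1) = FRC - RV = expiratory reserve volume (ERV)

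The inhaled litre cancels. The difference is zero only if one of the instructions is not followed as written.

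**3. Where each statement stands.**

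| Place | Starting volume | Says CT matches MRI |
|---|---|---|
| Synopsis, MDCT | FRC (CT) | yes |
| 4.1.6 and 6.6, MDCT | none given | yes |
| 4.1.2, MRI | none given | not about CT; 1H to match 129Xe |
| 6.7, MRI procedures | complete exhalation (129Xe) | not mentioned |

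The contradiction is therefore between section 6.7 and the synopsis. Nothing else in the document settles it.

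**4. Illustration of scale.** The documents give no FRC, RV or ERV values, so the following are assumptions. Take FRC = 2.5 L, so that CT is at 3.5 L, and let ERV range from 0.3 to 1.2 L. The MRI shortfall relative to CT is ERV / (FRC + 1).

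| Assumed ERV | RV = FRC - ERV | MRI volume | CT volume | Shortfall |
|---|---|---|---|---|
| 0.3 L | 2.2 L | 3.2 L | 3.5 L | 0.3/3.5 = 8.6% |
| 0.7 L | 1.8 L | 2.8 L | 3.5 L | 0.7/3.5 = 20% |
| 1.2 L | 1.3 L | 2.3 L | 3.5 L | 1.2/3.5 = 34% |

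These are differences in lung volume. They are not effects on VDP, on WA% or on their correlation, and the documents offer no way to convert one into the other.

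**The case against.** The strongest reply is that this is a wording slip and not a design flaw. The FRC start appears only in the synopsis. Sections 4.1.6 and 6.6 define the CT breath-hold by reference to MRI, so the body of the protocol read alone contains no mismatch. The intent to match is stated three times, and the team may well coach both scans identically. This stands in part: the documents do not show that any image was or will be acquired at a different volume. It does not remove the contradiction. The synopsis is current text, and someone following it together with section 6.7 would depart from the matching that the protocol promises.

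Two stronger readings are tempting and lack support. First, a reader might infer that the 1H scan is coached like CT while 129Xe starts from complete exhalation, so that a large share of the thoracic cavity would be misread as ventilation defect. Section 4.1.2 says the 1H scan is meant to match the 129Xe images, and nothing gives it a different starting volume, so that inference is conjecture. Second, a reader might infer that the VDP-WA% correlation is biased by a known amount, or that the second hypothesis rests on it alone. The documents give no basis for a size, and that hypothesis also relies on histology and does not name WA%.

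It is also fair to say that assumed percentages can be stretched by pairing a large reserve with a small FRC. The illustration above holds FRC fixed for that reason and carries no weight in the conclusion.

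**Conclusion.** The point holds as an internal contradiction in how image acquisition is specified. Followed as written, section 6.7 and the synopsis put 129Xe MRI and CT at lung volumes that differ by each participant's expiratory reserve. The stated CT-MRI matching behind the VDP, TCV and WA% comparisons would then not be delivered. The conclusion assumes only that complete exhalation means residual volume, which agrees with Appendix II, and that 1 L is inhaled in both cases.

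The size of the volume difference is not given in the documents, and its effect on the correlations is unknown. Whether practice departs from matching cannot be judged from the text. This is not a matter that an analysis plan could settle, because analysis cannot change the volume at which an image was acquired.

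**What to change.** Reconcile section 6.7 with the synopsis MDCT section. State one identical start-volume instruction for the 129Xe, 3He, 1H, CT and practice breath-holds, and repeat it or cross-refer to it in sections 4.1.2, 4.1.6 and 6.6. This review does not say which maneuver is right. The cost is one sentence and a shared coaching script, with no new procedure.

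Optionally, for data already acquired, compare MRI and CT lung volumes per participant as a sensitivity check on the CT-MRI analyses. Two cautions apply. TCV comes from the 1H scan, so agreement between TCV and CT volume would not reveal a mismatch confined to the 129Xe breath-hold. CT lung volume is not among the outputs named in section 8 and would have to be derived from the scans. Slow vital capacity minus inspiratory capacity, both provided for in Appendix II, would give an estimate of each participant's expiratory reserve. That measurement is taken seated, whereas imaging is supine.

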#### 7. STUDY PARAMETERS

#### 7.1. Evaluation of Disease

# 7.1.1. Pulmonary Function Testing

The FEV1 and FVC will be recorded according to ATS guidelines. Parameters to be assessed include but are not limited to: total lung capacity (TLC), functional residual capacity (FRC) and DLco. FRC measures the volume in the lungs when the muscles of respiration are relaxed. FOT measurements will be recorded according to ERS recommendations (Oostveen et al., Eur Respir J 2003; 22: 1026–1041). Input impedance is calculated as the ratio of pressure and flow signals and are given as Rrs and reactance Xrs at each oscillation frequency as well as comparison to predicted values. Additional outcomes that are provided from this measurement include tidal volume, respiratory rate, and resonant frequency.

Frequency dependence of Rrs is an index of ventilation heterogeneity, and low frequency reactance (6 Hz) can be used as an index of airway closure (Lutchen et al., 20xx) and we are investigating if this corresponds to the occurrence of ventilation defects. We will assess the frequency dependence by subtracting Rrs at 19 Hz from Rrs at 6 Hz. Furthermore, low frequency elastance at 6 Hz can be used as an index of airway closure indicative of the presence of low or near zero ventilation.

FeNO will be measured one time according to instructions from the machine which is set to perform to ATS guidelines. The FeNO value will be displayed on the machine and recorded in source documents, it is a valuable tool in the assessment of airway inflammation.

#### 7.1.2. MRI

During the gas administration and breath hold, all participants will be monitored using pulse oximetry for potential desaturation events. In the research setting at Robarts Research Institute, Xe gas is mixed with medical grade He and administered in a bag to volunteers for a single breath-hold; thus, the gas mixture in the research volunteer lung is hypoxic (containing no oxygen). The effects and safety profile of a single breath of

DATE: November 15, 2024

hypoxic gas have been assessed in thousands of participants worldwide with excellent tolerability results. The safety risk to participants and research volunteers stemming from the use of Xe gas contrast thus is directly related to: 1) the hypoxic nature of the gas mixture and not the actual content of the gas inhaled because the gas is chemically and physically inert and, 2) the length of the voluntary breath-hold (up to 16s maximum). With respect to the potential for oxygen desaturation events, at Robarts, participants are continuously monitored by pulse oximetry. Heart rate is also monitored using pulse oximetry. In addition, all participants will have oxygen nasal cannula in place during the MRI procedure. Supplemental oxygen will be administered at a flow rate of 2 L/m prior until immediately prior to administration of the hyperpolarized gas mixture. This "preoxygenation" procedure provides the lung with a greater amount of oxygen stored prior to breathing the single hypoxic breath, and minimizes any degree of desaturation that might occur. If a participant becomes uncomfortable during the maximum breath-hold of 16s they can breathe out the gas and subsequently breathe in room air and/or medical oxygen provided. Furthermore, in the event that oxygen saturation (monitored by pulse oximetry) during the MRI falls to below 88% for a period of > 10 seconds, all study participants will be administered an increase in supplemental oxygen. Moreover, research participants and volunteers may release the hypoxic breath-hold at any time and this effectively washes out the Xe and N2 immediately with room air and supplementary oxygen.

# 7.1.3. Hyperpolarized Xe Contrast

For imaging, a gas contrast agent is used - hyperpolarized Xe gas. The xenon component of a 99.25% medical grade Xe; 0.75% medical grade N2 mixture is polarized using a Xenon Hyperpolarizer Model 9800 (Polarean; XeniSpin, Durham NC, USA), until approximately 30% of the xenon is polarized. 5mL/kg (participant body weight) of this gas is mixed with medical grade He to form a 1L volume and is dispensed immediately to the participant through a sample bag and straw while the participant is supine in the scanner. Xe gas has been used in previous human studies at 0.5T, 1.5T and 3T with excellent safety and tolerability reported.

